18.9.4 EAIR of TEAEs: computation of Tier 1 and Tier 2 95% CIs

95%CI of the incidence rate will be computed using the GENMOD procedure from SAS ® with lsmeans instruction using a Poisson binomial model as follows:

```
ods listing close;
  proc genmod data=<Dataset>;
    where rate > 0;
    by <SOC/PT>;
    class <TreatmentGroup>;
    model rate = <TreatmentGroup> / dist=poisson link=log
    offset=log(PatientYears/1000);
    lsmeans <TreatmentGroup> / ilink cl;
    ods output lsmeans=OutLSmeans;
run;
ods listing;
```

[figure not shown]
where

<TreatmentGroup> represents the treatment group variable (usually TRT01AN)
<SOC/PT> represents the sorting variable (label for Overall, by SOC and by PT within SOC).

The 95%CI of difference with Placebo will be computed using MN method as follows:

```
proc freq data=<Dataset>;
  tables TreatmentGroup *AVALC / out=<outDataset> RISKDIFF (CL=MN) alpha=0.05;
  by AESOC AEDECOD;
  ods output PdiffCLs=<outPdiffCLs >;
run;
```

[figure not shown]
CCI

[figure not shown]
CCI

[figure not shown]
CCI

[figure not shown]
CCI

CCI

[figure not shown]
CCI

[figure not shown]
CCI

[figure not shown]
CCI

CCI

CCI

18.11 Time Windows

Table 51: Time Windows for SFI, SLEDAI-2K, PGA, BILAG 2004

Analysis	Treatment groups	Period covered	Interval (days) [Date of assessment – Date of first dose + 1]	Analysis Visit

 PA Japanese cohort analysis 	
 Placebo Evobrutinib 25 mg QD Evobrutinib 75 mg QD Evobrutinib 50 mg BID 	52-week treatment period	1	Day 1
			[2 ; 42)	Week 4 – Day 29
			[42 ; 70)	Week 8 – Day 57
			[70 ; 98)	Week 12 – Day 85
			[98 ; 126)	Week 16 – Day 113
			[126 ; 154)	Week 20 – Day 141
			[154 ; 182)	Week 24 – Day 169
			[182 ; 210)	Week 28 – Day 197
			[210 ; 238)	Week 32 – Day 225
			[238 ; 266)	Week 36 – Day 253
			[266 ; 294)	Week 40 – Day 281
			[294 ; 322)	Week 44 – Day 309
			[322 ; 350)	Week 48 – Day 337
≥ 350*	Week 52 – Day 365			

 LTE analysis 	
 Placebo/Evobrutinib 50 mg BID Evobrutinib 25 mg QD/Evobrutinib 50 mg BID Evobrutinib 75 mg QD/Evobrutinib 50 mg BID Evobrutinib 50 mg BID/Evobrutinib 50 mg BID 	52-week treatment period	NA	NA
		LTE period	1	Day 1 – LTE
			[2 ; 266)	Week 24 - Day 169 – LTE
			[266 ; 554)	Week 52 - Day 365 – LTE
			[554 ; 751)	Week 104 - Day 745 – LTE

* Assessments performed more than 14 days after last exposure date will not be included as well as assessments collected during safety follow-up visit.

Table 52: Time Windows for CLASI

Analysis	Treatment groups	Period covered	Interval (days) [Date of assessment – Date of first dose + 1]	Analysis Visit
• PA	
 • Placebo • Evobrutinib 25 mg QD • Evobrutinib 75 mg QD • Evobrutinib 50 mg BID 	52-week treatment period	1	Day 1
			[2 ; 21)	Week 2 – Day 15
			[21 ; 42)	Week 4 – Day 29
			[42 ; 70)	Week 8 – Day 57
			[70 ; 98)	Week 12 – Day 85
			[98 ; 126)	Week 16 – Day 113
			[126 ; 154)	Week 20 – Day 141
			[154 ; 182)	Week 24 – Day 169
			[182 ; 210)	Week 28 – Day 197
			[210 ; 238)	Week 32 – Day 225
			[238 ; 266)	Week 36 – Day 253
			[266 ; 294)	Week 40 – Day 281
			[294 ; 322)	Week 44 – Day 309
[322 ; 350)	Week 48 – Day 337			
	≥ 350*	Week 52 – Day 365		
• LTE analysis	
 • Placebo/Evobrutinib 50 mg BID • Evobrutinib 25 mg QD/Evobrutinib 50 mg BID • Evobrutinib 75 mg QD/Evobrutinib 50 mg BID • Evobrutinib 50 mg BID/Evobrutinib 50 mg BID 	52-week treatment period	NA	NA
		LTE period	1	Day 1 – LTE
			[2 ; 266)	Week 24 - Day 169 – LTE
			[266 ; 554)	Week 52 - Day 365 – LTE
	[554 ; 751)	Week 104 - Day 745 – LTE		

* Assessments performed more than 14 days after last exposure date will not be included as well as assessments collected during safety follow-up visit.

Table 53: Time Windows for Urinalysis, Hematology, Chemistry

Analysis	Treatment groups	Period covered	Interval (days) [Date of assessment – Date of first dose + 1]	Analysis Visit
• PA	
 • Placebo • Evobrutinib 25 mg QD • Evobrutinib 75 mg QD • Evobrutinib 50 mg BID 	52-week treatment period	1	Day 1
			[2 ; 21)	Week 2 – Day 15
			[21 ; 42)	Week 4 – Day 29
			[42 ; 70)	Week 8 – Day 57
			[70 ; 98)	Week 12 – Day 85
			[98 ; 126)	Week 16 – Day 113
			[126 ; 154)	Week 20 – Day 141
			[154 ; 182)	Week 24 – Day 169
			[182 ; 210)	Week 28 – Day 197
			[210 ; 238)	Week 32 – Day 225
			[238 ; 266)	Week 36 – Day 253
			[266 ; 294)	Week 40 – Day 281
			[294 ; 322)	Week 44 – Day 309
[322 ; 350)	Week 48 – Day 337			
		≥ 350*	Week 52 – Day 365	
• LTE analysis	
 • Placebo/Evobrutinib 50 mg BID • Evobrutinib 25 mg QD/Evobrutinib 50 mg BID • Evobrutinib 75 mg QD/Evobrutinib 50 mg BID • Evobrutinib 50 mg BID/Evobrutinib 50 mg BID 	52-week treatment period	NA	NA
		LTE period	1	Day 1 – LTE
			[2 ; 42)	Week 4 - Day 29 – LTE
			[42 ; 70)	Week 8 - Day 57 – LTE
			[70 ; 126)	Week 12 - Day 85 – LTE
			[126 ; 224)	Week 24 - Day 169 – LTE
			[224 ; 322)	Week 40 - Day 281 – LTE
			[322 ; 454)	Week 52 - Day 365 – LTE
			[454 ; 644)	Week 76 - Day 545 – LTE
			[644 ; 751)	Week 104 - Day 745 – LTE

* Assessments performed more than 14 days after last exposure date will not be included as well as assessments collected during safety follow-up visit.

Table 54: Time Windows for Urine Microscopy, UPCR

Analysis	Treatment groups	Period covered	Interval (days) [Date of assessment – Date of first dose + 1]	Analysis Visit
• PA	
 • Placebo • Evobrutinib 25 mg QD • Evobrutinib 75 mg QD • Evobrutinib 50 mg BID 	52-week treatment period	1	Day 1
			[2 ; 21)	Week 2 – Day 15
			[21 ; 42)	Week 4 – Day 29
			[42 ; 70)	Week 8 – Day 57
			[70 ; 98)	Week 12 – Day 85
			[98 ; 126)	Week 16 – Day 113
			[126 ; 154)	Week 20 – Day 141
			[154 ; 182)	Week 24 – Day 169
			[182 ; 210)	Week 28 – Day 197
			[210 ; 238)	Week 32 – Day 225
			[238 ; 266)	Week 36 – Day 253
			[266 ; 294)	Week 40 – Day 281
			[294 ; 322)	Week 44 – Day 309
[322 ; 350)	Week 48 – Day 337			
	≥ 350*	Week 52 – Day 365		
• LTE analysis	
 • Placebo/Evobrutinib 50 mg BID • Evobrutinib 25 mg QD/Evobrutinib 50 mg BID • Evobrutinib 75 mg QD/Evobrutinib 50 mg BID • Evobrutinib 50 mg BID/Evobrutinib 50 mg BID 	52-week treatment period	NA	NA
		LTE period	1	Day 1 – LTE
			[2 ; 266)	Week 24 - Day 169 – LTE
			[266 ; 554)	Week 52 - Day 365 – LTE
		[554 ; 751)	Week 104 - Day 745 – LTE	

* Assessments performed more than 14 days after last exposure date will not be included as well as assessments collected during safety follow-up visit.

Table 55: Time Windows for Supplementary Liver Function Tests (LFTs)

Analysis	Treatment groups	Period covered	Interval (days) [Date of assessment – Date of first dose + 1]	Analysis Visit
• PA	
 • Placebo • Evobrutinib 25 mg QD • Evobrutinib 75 mg QD • Evobrutinib 50 mg BID 	52-week treatment period	1	Day 1
			[2 ; 21)	Week 2 – Day 15
			[21 ; 35)	Week 4 – Day 29
			[35 ; 49)	Week 6 – Day 43
			[49 ; 63)	Week 8 – Day 57
			[63 ; 77)	Week 10 – Day 71
			[77 ; 91)	Week 12 – Day 85
			[91 ; 105)	Week 14 – Day 99
			[105 ; 126)	Week 16 – Day 113
			[126 ; 154)	Week 20 – Day 141
			[154 ; 182)	Week 24 – Day 169
			[182 ; 210)	Week 28 – Day 197
			[210 ; 238)	Week 32 – Day 225
			[238 ; 266)	Week 36 – Day 253
[266 ; 294)	Week 40 – Day 281			
[294 ; 322)	Week 44 – Day 309			
[322 ; 350)	Week 48 – Day 337			
≥ 350*	Week 52 – Day 365			
• LTE analysis	
 • Placebo/Evobrutinib 50 mg BID • Evobrutinib 25 mg QD/Evobrutinib 50 mg BID • Evobrutinib 75 mg QD/Evobrutinib 50 mg BID • Evobrutinib 50 mg BID/Evobrutinib 50 mg BID 	52-week treatment period	NA	NA
		LTE period	1	Day 1 – LTE
			[2 ; 21)	Week 2 - Day 15 – LTE
			[21 ; 35)	Week 4 - Day 29 – LTE
			[35 ; 49)	Week 6 - Day 43 – LTE
			[49 ; 63)	Week 8 - Day 57 – LTE
			[63 ; 77)	Week 10 - Day 71 – LTE
			[77 ; 91)	Week 12 - Day 85 – LTE
			[91 ; 105)	Week 14 - Day 99 – LTE
			[105 ; 140)	Week 16 - Day 113 – LTE
			[140 ; 224)	Week 24 - Day 169 – LTE
			[224 ; 322)	Week 40 - Day 281 – LTE
			[322 ; 454)	Week 52 - Day 365 – LTE
			[454 ; 644)	Week 76 - Day 545 – LTE
			[644 ; 751)	Week 104 - Day 745 – LTE

* Assessments performed more than 14 days after last exposure date will not be included as well as assessments collected during safety follow-up visit.

Table 56: Time Windows for Total Ig Levels (IgG, IgA, IgM) and IgG^{CCI}

Analysis	Treatment groups	Period covered	Interval (days) [Date of assessment – Date of first dose + 1]	Analysis Visit
• PA	
 • Placebo • Evobrutinib 25 mg QD • Evobrutinib 75 mg QD • Evobrutinib 50 mg BID 	52-week treatment period	1	Day 1
			[2 ; 21)	Week 2 – Day 15
			[21 ; 42)	Week 4 – Day 29
			[42 ; 126)	Week 12 – Day 85
			[126 ; 210)	Week 24 – Day 169
			[210 ; 308)	Week 36 – Day 253
			≥ 308*	Week 52 – Day 365
• LTE analysis	
 • Placebo/Evobrutinib 50 mg BID • Evobrutinib 25 mg QD/Evobrutinib 50 mg BID • Evobrutinib 75 mg QD/Evobrutinib 50 mg BID • Evobrutinib 50 mg BID/Evobrutinib 50 mg BID 	52-week treatment period	NA	NA
		LTE period	1	Day 1 – LTE
			[2 ; 42)	Week 4 - Day 29 – LTE
			[42 ; 70)	Week 8 - Day 57 – LTE
			[70 ; 126)	Week 12 - Day 85 – LTE
			[126 ; 224)	Week 24 - Day 169 – LTE
			[224 ; 322)	Week 40 - Day 281 – LTE
			[322 ; 454)	Week 52 - Day 365 – LTE
			[454 ; 644)	Week 76 - Day 545 – LTE
[644 ; 751)	Week 104 - Day 745 – LTE			

CCI

* Assessments performed more than 14 days after last exposure date will not be included as well as assessments collected during safety follow-up visit.

Table 57: Time Windows for SF-36v2, LupusQoL, FACIT-Fatigue, EQ-5D-5L

Analysis	Treatment groups	Period covered	Interval (days) [Date of assessment – Date of first dose + 1]	Analysis Visit
• PA	
 • Placebo • Evobrutinib 25 mg QD • Evobrutinib 75 mg QD • Evobrutinib 50 mg BID 	52-week treatment period	1	Day 1
			[2 ; 42)	Week 4 – Day 29
			[42 ; 70)	Week 8 – Day 57
			[70 ; 98)	Week 12 – Day 85
			[98 ; 140)	Week 16 – Day 113
			[140 ; 196)	Week 24 – Day 169
			[196 ; 252)	Week 32 – Day 225
			[252 ; 322)	Week 40 – Day 281
	≥ 322*	Week 52 – Day 365		
• LTE analysis	
 • Placebo/Evobrutinib 50 mg BID • Evobrutinib 25 mg QD/Evobrutinib 50 mg BID • Evobrutinib 75 mg QD/Evobrutinib 50 mg BID • Evobrutinib 50 mg BID/Evobrutinib 50 mg BID 	52-week treatment period	NA	NA
		LTE period	1	Day 1 – LTE
			[2 ; 266)	Week 24 - Day 169 – LTE
			[266 ; 554)	Week 52 - Day 365 – LTE
	[554 ; 751)	Week 104 - Day 745 – LTE		

* Assessments performed more than 14 days after last exposure date will not be included as well as assessments collected during safety follow-up visit.

Table 58: Time Windows for HRU

Analysis	Treatment groups	Period covered	Interval (days) [Date of assessment – Date of first dose + 1]	Analysis Visit
• PA	
 • Placebo • Evobrutinib 25 mg QD • Evobrutinib 75 mg QD • Evobrutinib 50 mg BID 	52-week treatment period	[1 ; 42)	Week 4 – Day 29
			[42 ; 70)	Week 8 – Day 57
			[70 ; 98)	Week 12 – Day 85
			[98 ; 126)	Week 16 – Day 113
			[126 ; 154)	Week 20 – Day 141
			[154 ; 182)	Week 24 – Day 169
			[182 ; 210)	Week 28 – Day 197
			[210 ; 238)	Week 32 – Day 225
			[238 ; 266)	Week 36 – Day 253
			[266 ; 294)	Week 40 – Day 281
			[294 ; 322)	Week 44 – Day 309
[322 ; 350)	Week 48 – Day 337			
	≥ 350*	Week 52 – Day 365		
• LTE analysis	
 • Placebo/Evobrutinib 50 mg BID • Evobrutinib 25 mg QD/Evobrutinib 50 mg BID • Evobrutinib 75 mg QD/Evobrutinib 50 mg BID • Evobrutinib 50 mg BID/Evobrutinib 50 mg BID 	52-week treatment period	NA	NA
		LTE period	1	Day 1 – LTE
			[2 ; 42)	Week 4 - Day 29 – LTE
			[42 ; 70)	Week 8 - Day 57 – LTE
			[70 ; 98)	Week 12 - Day 85 – LTE
			[98 ; 140)	Week 16 - Day 113 – LTE
			[140 ; 224)	Week 24 - Day 169 – LTE
			[224 ; 322)	Week 40 - Day 281 – LTE
			[322 ; 454)	Week 52 - Day 365 – LTE
			[454 ; 644)	Week 76 - Day 545 – LTE
[644 ; 751)	Week 104 - Day 745 – LTE			

* Assessments performed more than 14 days after last exposure date will not be included as well as assessments collected during safety follow-up visit.

Table 59: Time Windows for Vital Signs

Analysis	Treatment groups	Period covered	Interval (days) [Date of assessment – Date of first dose + 1]	Analysis Visit
• PA	
 • Placebo • Evobrutinib 25 mg QD • Evobrutinib 75 mg QD • Evobrutinib 50 mg BID 	52-week treatment period	1	Day 1
			[2 ; 21)	Week 2 – Day 15
			[21 ; 42)	Week 4 – Day 29
			[42 ; 70)	Week 8 – Day 57
			[70 ; 98)	Week 12 – Day 85
			[98 ; 126)	Week 16 – Day 113
			[126 ; 154)	Week 20 – Day 141
			[154 ; 182)	Week 24 – Day 169
			[182 ; 210)	Week 28 – Day 197
			[210 ; 238)	Week 32 – Day 225
			[238 ; 266)	Week 36 – Day 253
			[266 ; 294)	Week 40 – Day 281
			[294 ; 322)	Week 44 – Day 309
			[322 ; 350)	Week 48 – Day 337
≥ 350*	Week 52 – Day 365			
• LTE analysis	
 • Placebo/Evobrutinib 50 mg BID • Evobrutinib 25 mg QD/Evobrutinib 50 mg BID • Evobrutinib 75 mg QD/Evobrutinib 50 mg BID • Evobrutinib 50 mg BID/Evobrutinib 50 mg BID 	52-week treatment period	NA	NA
		LTE period	1	Day 1 – LTE
			[2 ; 42)	Week 4 - Day 29 – LTE
			[42 ; 70)	Week 8 - Day 57 – LTE
			[70 ; 98)	Week 12 - Day 85 – LTE
			[98 ; 140)	Week 16 - Day 113 – LTE
			[140 ; 224)	Week 24 - Day 169 – LTE
			[224 ; 322)	Week 40 - Day 281 – LTE
			[322 ; 454)	Week 52 - Day 365 – LTE
			[454 ; 644)	Week 76 - Day 545 – LTE
[644 ; 751)	Week 104 - Day 745 – LTE			

* Assessments performed more than 14 days after last exposure date will not be included as well as assessments collected during safety follow-up visit.

Table 60: Time Windows for PGIC

Analysis	Treatment groups	Period covered	Interval (days) [Date of assessment – Date of first dose + 1]	Analysis Visit
• PA	
 • Placebo • Evobrutinib 25 mg QD • Evobrutinib 75 mg QD • Evobrutinib 50 mg BID 	52-week treatment period	[1 ; 42)	Week 4 – Day 29
			[42 ; 70)	Week 8 – Day 57
			[70 ; 98)	Week 12 – Day 85
			[98 ; 140)	Week 16 – Day 113
			[140 ; 196)	Week 24 – Day 169
			[196 ; 252)	Week 32 – Day 225
			[252 ; 322)	Week 40 – Day 281
≥ 322*	Week 52 – Day 365			
• LTE analysis	
 • Placebo/Evobrutinib 50 mg BID • Evobrutinib 25 mg QD/Evobrutinib 50 mg BID • Evobrutinib 75 mg QD/Evobrutinib 50 mg BID • Evobrutinib 50 mg BID/Evobrutinib 50 mg BID 	52-week treatment period	NA	NA
		LTE period	1	Day 1 – LTE
			[2 ; 266)	Week 24 - Day 169 – LTE
			[266 ; 554)	Week 52 - Day 365 – LTE
		[554 ; 751)	Week 104 - Day 745 – LTE	

* Assessments performed more than 14 days after last exposure date will not be included as well as assessments collected during safety follow-up visit.

Table 61: Time Windows for ECG

Analysis	Treatment groups	Period covered	Interval (days) [Date of assessment – Date of first dose + 1]	Analysis Visit
• PA	
 • Placebo • Evobrutinib 25 mg QD • Evobrutinib 75 mg QD • Evobrutinib 50 mg BID 	52-week treatment period	1	Day 1
			[2 ; 126)	Week 12 – Day 85
			[126 ; 224)	Week 24 – Day 169
			[224 ; 322)	Week 40 – Day 281
			≥ 322*	Week 52 – Day 365
• LTE analysis	
 • Placebo/Evobrutinib 50 mg BID • Evobrutinib 25 mg QD/Evobrutinib 50 mg BID • Evobrutinib 75 mg QD/Evobrutinib 50 mg BID • Evobrutinib 50 mg BID/Evobrutinib 50 mg BID 	52-week treatment period	NA	NA
		LTE period	1	Day 1 – LTE
			[2 ; 126)	Week 12 - Day 85 – LTE
			[126 ; 266)	Week 24 - Day 169 – LTE
			[266 ; 454)	Week 52 - Day 365 – LTE
			[454 ; 644)	Week 76 - Day 545 – LTE
[644 ; 751)	Week 104 - Day 745 – LTE			

* Assessments performed more than 14 days after last exposure date will not be included as well as assessments collected during safety follow-up visit.

[figure not shown]

Table 62: Time Windows for C-SSRS

Analysis	Treatment groups	Period covered	Interval (days) [Date of assessment – Date of first dose + 1]	Analysis Visit
• PA	
 • Placebo • Evobrutinib 25 mg QD • Evobrutinib 75 mg QD • Evobrutinib 50 mg BID 	52-week treatment period	[1 ; 56)	Week 4 – Day 29
			[56 ; 112)	Week 12 – Day 85
			[112 ; 168)	Week 20 – Day 141
			[168 ; 224)	Week 28 – Day 197
			[224 ; 280)	Week 36 – Day 253
			[280 ; 336)	Week 44 – Day 309
		≥ 336*	Week 52 – Day 365	
• LTE analysis	
 • Placebo/Evobrutinib 50 mg BID • Evobrutinib 25 mg QD/Evobrutinib 50 mg BID • Evobrutinib 75 mg QD/Evobrutinib 50 mg BID • Evobrutinib 50 mg BID/Evobrutinib 50 mg BID 	52-week treatment period	NA	NA
		LTE period	1	Day 1 – LTE
			[2 ; 126)	Week 12 - Day 85 – LTE
			[126 ; 266)	Week 24 - Day 169 – LTE
			[266 ; 454)	Week 52 - Day 365 – LTE
			[454 ; 644)	Week 76 - Day 545 – LTE
[644 ; 751)	Week 104 - Day 745 – LTE			

* Assessments performed more than 14 days after last exposure date will not be included as well as assessments collected during safety follow-up visit.

Table 63: Time Windows for SLICC/ACR Damage Index

Analysis	Treatment groups	Period covered	Interval (days) [Date of assessment – Date of first dose + 1]	Analysis Visit
• PA	
 • Placebo • Evobrutinib 25 mg QD • Evobrutinib 75 mg QD • Evobrutinib 50 mg BID 	52-week treatment period	1	Day 1
			≥ 2*	Week 52 – Day 365
• LTE analysis	
 • Placebo/Evobrutinib 50 mg BID • Evobrutinib 25 mg QD/Evobrutinib 50 mg BID • Evobrutinib 75 mg QD/Evobrutinib 50 mg BID • Evobrutinib 50 mg BID/Evobrutinib 50 mg BID 	52-week treatment period	NA	NA
		LTE period	1	Day 1 – LTE
			[2 ; 266)	Week 24 - Day 169 – LTE
			[266 ; 554)	Week 52 - Day 365 – LTE
		[554 ; 751)	Week 104 - Day 745 – LTE	

* Assessments performed more than 14 days after last exposure date will not be included as well as assessments collected during safety follow-up visit.

Table 64: Time Windows for Total B Cell Count

Analysis	Treatment groups	Period covered	Interval (days) [Date of assessment – Date of first dose + 1]	Analysis Visit
• PA	
 • Placebo • Evobrutinib 25 mg QD • Evobrutinib 75 mg QD • Evobrutinib 50 mg BID 	52-week treatment period	1	Day 1
			[2 ; 84)	Week 4 – Day 29
			[84 ; 266)	Week 24 – Day 169
			≥ 266*	Week 52 – Day 365
• LTE analysis	
 • Placebo/Evobrutinib 50 mg BID • Evobrutinib 25 mg QD/Evobrutinib 50 mg BID • Evobrutinib 75 mg QD/Evobrutinib 50 mg BID • Evobrutinib 50 mg BID/Evobrutinib 50 mg BID 	52-week treatment period	NA	NA
		LTE period	1	Day 1 – LTE
			[2 ; 84)	Week 4 - Day 29 – LTE
			[84 ; 266)	Week 24 - Day 169 – LTE
			[266 ; 554)	Week 52 - Day 365 – LTE
[554 ; 751)	Week 104 - Day 745 – LTE			
* Assessments performed more than 14 days after last exposure date will not be included as well as assessments collected during safety follow-up visit.				

CCI

Table 66: Time Windows for Autoantibodies, anti-Sm

Analysis	Treatment groups	Period covered	Interval (days) [Date of assessment – Date of first dose + 1]	Analysis Visit
• PA	
 • Placebo • Evobrutinib 25 mg QD • Evobrutinib 75 mg QD • Evobrutinib 50 mg BID 	52-week treatment period	1	Day 1
			[2 ; 266)	Week 24 – Day 169
			≥ 266*	Week 52 – Day 365
• LTE analysis	
 • Placebo/Evobrutinib 50 mg BID • Evobrutinib 25 mg QD/Evobrutinib 50 mg BID • Evobrutinib 75 mg QD/Evobrutinib 50 mg BID • Evobrutinib 50 mg BID/Evobrutinib 50 mg BID 	52-week treatment period	NA	NA
		LTE period	1	Day 1 – LTE
			[2 ; 266)	Week 24 - Day 169 – LTE
			[266 ; 554)	Week 52 - Day 365 – LTE
[554 ; 751)	Week 104 - Day 745 – LTE			
* Assessments performed more than 14 days after last exposure date will not be included as well as assessments collected during safety follow-up visit.				

Table 67: Time Windows for ANA

Analysis	Treatment groups	Period covered	Interval (days) [Date of assessment – Date of first dose + 1]	Analysis Visit
• PA	
 • Placebo • Evobrutinib 25 mg QD • Evobrutinib 75 mg QD • Evobrutinib 50 mg BID 	52-week treatment period	1	Day 1
• LTE analysis	
 • Placebo/Evobrutinib 50 mg BID • Evobrutinib 25 mg QD/Evobrutinib 50 mg BID • Evobrutinib 75 mg QD/Evobrutinib 50 mg BID • Evobrutinib 50 mg BID/Evobrutinib 50 mg BID 	52-week treatment period	NA	NA
		LTE period	1	Day 1 – LTE
			[2 ; 266)	Week 24 - Day 169 – LTE
			[266 ; 554)	Week 52 - Day 365 – LTE
[554 ; 751)	Week 104 - Day 745 – LTE			

CCI

Table 69: Time Windows for HBV DNA assessments

Analysis	Treatment groups	Period covered	Interval (days) [Date of assessment – Date of first dose + 1]	Analysis Visit
• PA	
 • Placebo • Evobrutinib 25 mg QD • Evobrutinib 75 mg QD • Evobrutinib 50 mg BID 	52-week treatment period	[2 ; 42)	Week 4 – Day 29
			[42 ; 70)	Week 8 – Day 57
			[70 ; 98)	Week 12 – Day 85
			[98 ; 126)	Week 16 – Day 113
			[126 ; 154)	Week 20 – Day 141
			[154 ; 182)	Week 24 – Day 169
			[182 ; 266)	Week 36 – Day 253
			[266 ; 350)	Week 48 – Day 337
	≥ 350*	Week 52 – Day 365		
• LTE	• Placebo/Evobrutinib 50	52-week treatment period	NA	NA

analysis	mg BID	LTE period	1	Day 1 – LTE
			[2 ; 35)	Week 4 – Day 29 - LTE

 Evobrutinib 25 mg QD/Evobrutinib 50 mg BID 	
 Evobrutinib 75 mg QD/Evobrutinib 50 mg BID 	
 Evobrutinib 50 mg BID/Evobrutinib 50 mg BID 	[35 ; 63)	Week 8 – Day 57 - LTE
			[63 ; 91)	Week 12 – Day 85 - LTE
			[91 ; 140)	Week 16 - Day 113 – LTE
			[140 ; 224)	Week 24 - Day 169 – LTE
			[224 ; 322)	Week 40 - Day 281 – LTE
			[322 ; 454)	Week 52 - Day 365 – LTE
			[454 ; 644)	Week 76 - Day 545 – LTE
			[644 ; 751)	Week 104 - Day 745 – LTE

* Assessments performed more than 14 days after last exposure date will not be included as well as assessments collected during safety follow-up visit.

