If the System Organ Class (SOC) or Anatomical Therapeutic Class (ATC) term is missing/not coded yet, then ‘Uncoded SOC’ (or ‘Uncoded ATC’) will be indicated at the TLF level. When a Preferred Term (PT) is missing, it will be set to ‘Uncoded PT: verbatim text’.

Treatment day:

Treatment day is defined as relative day to the start date of treatment. Treatment day will be calculated as the number of days since the first administration of any IMP. The day before is defined as Treatment day –1 (no Treatment day 0 is defined). Treatment day will only be presented in subject safety data listings.

For the 52-week treatment period, start date of treatment is defined as the date of first administration of randomized study drug.

For the LTE treatment period, start date of treatment is defined as the date of first treatment administration on or after the date of end of 52-week treatment.

On-Treatment flag:

On-treatment values are results of assessments done from the first IMP administration on Day 1 till End of Study (completion or early termination).

Repeated and unscheduled measurements:

Repeated and unscheduled measurements are included in the listings. Data collected at both unscheduled and scheduled visits will be used for shift tables. For summary statistics, figures, or inferential analysis, data are re-allocated to an analysis visit using time window calculations (see below).

Gap between 52-Week treatment period and LTE treatment period:

Subjects with a gap greater than or equal to 2 weeks between 52-Week treatment period and LTE period will be analyzed the same way as subjects without a gap. The gap will be defined using the last dose received during the 52-week treatment period and the first dose received during the LTE treatment period. Specific data listings on safety data (AEs and laboratory data) collected during the gap period will be produced for these subjects for the LTE analysis. In addition, for the subgroup of subjects with a gap greater than or equal to 2 weeks, the following analyses will be provided:

- Summary statistics of the gap duration
- SLE disease baseline characteristics at LTE Day 1
- SRI-4 response and SRI-6 response among HDA subjects by LTE visit

Time windows:

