For efficacy and safety analyses, each measurement will be assigned an analysis visit number first according to the prespecified time window. The analysis visit will then be used for missing data imputations, analysis variable derivations, statistical calculations and presentations. Safety follow-up will not be included in analysis visit calculations, only assessments collected under treatment visits and no more than 14 days after last exposure date will be used.

For by visit summary of safety endpoints (e.g. laboratory and vital sign assessments), data collected during the safety follow-up will be shown, presenting separately data from subjects who completed safety follow-up and who discontinued during safety follow-up.

For subject data listings by time point, the nominal visit (as collected in the database) as well as the analysis visit will be displayed.

For the calculation of analysis visit using the time windows, 1 month is expressed as 30 days.

[figure not shown]
As the schedule of assessments is different for each visit, specific time windows must be used for each endpoint. They are defined in Appendix 18.11.

If there are multiple assessments within a same visit window, then the one closest to the target day will be used. If two assessments have the same difference with target day, the earlier one will be used.

Unblinding:

Details regarding the unblinding process are available in the Unblinding Plan.

CCI

10 Trial Subjects

The subsections in this section include specifications for reporting subject disposition and treatment/trial discontinuations. Additionally, procedures for reporting protocol deviations are provided.

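### Eight visit-window limits in SAP Tables 56, 64 and 69 do not fit those tables' own visits, so late safety samples can be labelled as the next visit

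*SAP*

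**What the plan says.** Section 9.7 (Time windows) sets the order of steps. First, "each measurement will be assigned an analysis visit number first according to the prespecified time window". Then, "If there are multiple assessments within a same visit window, then the one closest to the target day will be used". It refers to Appendix 18.11 for windows specific to each endpoint's schedule. It states no formula for the limits.

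The windows at issue in Appendix 18.11 are:

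- **Table 69 (HBV DNA), LTE:** "2 ; 35) Week 4 – Day 29 - LTE", then limits of 63 and 91 before Weeks 12 and 16.
- **Table 69, PA:** Week 24 ends before Day 182, then "182 ; 266) Week 36 – Day 253", with Week 48 starting at Day 266.
- **Table 56 (immunoglobulins), PA:** Week 4 ends before Day 42, then "42 ; 126) Week 12 – Day 85".
- **Table 64 (total B cells), PA and LTE:** Week 4 ends before Day 84. The LTE row that follows is "84 ; 266) Week 24 - Day 169 – LTE".

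For comparison, the LTE rows of Tables 58 and 59 have the same Week 4, 8, 12 and 16 visits as Table 69 LTE and use "42 ; 70) Week 8 - Day 57 – LTE", followed by limits of 98 and 140.

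**The concern.** For the same pair of neighbouring visits, different tables give different limits. Most of the odd limits match a denser schedule. The values 35, 63 and 91 are the Week 4/6, 8/10 and 12/14 limits of the two-weekly liver-test schedule in Table 55, but Table 69 has no Week 6, 10 or 14. The values 182 and 266 are the Week 24/28 and 36/40 limits of the four-weekly schedule in Table 51, but Table 69 PA has no Week 28 or 40. The value 42 is the usual Week 4/8 limit, but Table 56 PA has no Week 8.

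Because labelling comes before selection, the closest-to-target rule cannot repair a wrong label. It can only discard the relabelled sample or keep it under the wrong visit. At stake are the by-time-point displays of HBV DNA (Section 15.13), immunoglobulins (Section 15.8) and B cells (Section 15.9). The last two are listed among the primary safety endpoints in Table 1.

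**Working it through.** **Inputs.** Printed target days and limits from the readable window tables in Appendix 18.11, and the two-step rule in Section 9.7.

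**Step 1: the document's usual pattern.** For neighbouring target days t1 and t2, compare the printed limit with (t1 + t2)/2 − 1. For example, Days 29 and 57 give 43 − 1 = 42. Counting each repeated visit pattern once, 109 of 117 limits equal this value. The 8 exceptions are five in Table 69, one in Table 56 PA, and the day-84 limit in both halves of Table 64.

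**Step 2: the exceptions.**

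| Table | Visits (target days) | Printed | Midpoint − 1 | Same pair elsewhere |
|---|---|---|---|---|
| 69 LTE | Wk 4/8 (29, 57) | 35 | 43 − 1 = 42 | 42: Table 69 PA, Tables 58/59 LTE |
| 69 LTE | Wk 8/12 (57, 85) | 63 | 71 − 1 = 70 | 70: same tables |
| 69 LTE | Wk 12/16 (85, 113) | 91 | 99 − 1 = 98 | 98: same tables |
| 69 PA | Wk 24/36 (169, 253) | 182 | 211 − 1 = 210 | 210: Table 56 PA |
| 69 PA | Wk 36/48 (253, 337) | 266 | 295 − 1 = 294 | none |
| 56 PA | Wk 4/12 (29, 85) | 42 | 57 − 1 = 56 | 56: Table 62 PA |
| 64 PA and LTE | Wk 4/24 (29, 169) | 84 | 99 − 1 = 98 | none |

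**Step 3: days that change label under the usual pattern.**

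- Table 69 LTE: Days 35–41, 63–69 and 91–97, so 7 of each 28-day interval.
- Table 69 PA: Days 182–209 and 266–293, so 28 of each 84.
- Table 56 PA: Days 42–55, so 14 of 56.
- Table 64: Days 84–97, so 14 of 140.

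One further day per limit is also nearer the earlier visit. Day 42, for example, is 13 days from Day 29 and 15 from Day 57. The usual pattern labels that day as the later visit in every table, so it is not counted here.

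**Step 4: how late a sample must be.**

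- Table 69 LTE: 35 − 29 = 6 days late, with the next target 57 − 35 = 22 days away.
- Table 69 PA: 182 − 169 = 13 days late, next target 71 days away. The Week 36/48 limit gives the same distances.
- Table 56 PA: 42 − 29 = 13 days late, next target 43 days away.
- Table 64: 84 − 29 = 55 days late, next target 85 days away.

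**Step 5: consequence under Section 9.7.** Take LTE HBV DNA samples on Days 35 and 57. Both fall in the printed Week 8 window, at distances 22 and 0. Day 57 is kept, and Week 4 is missing if Day 35 was its only sample. If there is no Week 8 sample, Day 35 is reported as Week 8.

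A subject who is always 6 days late (Days 35, 63, 91, 119) is labelled Weeks 8, 12, 16 and 16. Week 4 is empty, and Day 119 (distance 6) displaces Day 91 (distance 22). With limits 42, 70 and 98 the same four samples are labelled Weeks 4, 8, 12 and 16.

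**Step 6: displacement when a genuine next-visit sample exists.** Let that sample fall on any day from the midpoint to the end of its window, and weight all day combinations equally. The relabelled sample then loses in 100% of combinations for limits 35, 63, 182 and 266, in 92.5% for 42 in Table 56, in 89% for 84, and in 79% for 91. These shares include the one further day per limit noted in Step 3.

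**The case against.** **No written rule is broken.** This stands: the SAP never states a midpoint rule. The point rests on a pattern that holds in 109 of 117 limits and, for five of the eight exceptions, on a different limit for the same visit pair elsewhere in the appendix. The Week 36/48 limit and the two day-84 limits rest on the pattern alone.

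**A reader might infer that relabelled samples are mostly lost.** The SAP does not support that. Loss of a visit's value needs both a late sample that is the only one for its visit and a genuine next-visit sample. An early-termination sample usually has no later sample, so it is kept under the wrong label. An extra Day 38 sample, taken when Day 29 and Week 8 samples also exist, goes unused under either limit.

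**A reader might put a percentage on it.** If LTE visit dates scattered around target with an SD of 3, 4 or 7 days, 1 − Φ((34.5 − 29)/SD) would give 3%, 8% or 22% of Week 4 samples labelled Week 8. The SAP gives no such spread. Section 15.3 adds 5 days to the Week 56 follow-up day in a censoring rule. If LTE visits carried a similar +5-day tolerance (an assumption), the latest in-tolerance samples would fall on Days 34, 62 and 90, and all would be labelled correctly.

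**A reader might infer that HBV reactivation could be hidden.** It would not be. Section 15.13 also plans a shift table to the highest post-baseline value, and Section 9.7 says "Data collected at both unscheduled and scheduled visits will be used for shift tables". Listings show both nominal and analysis visit.

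**Parts of Table 56 are redacted.** Text in its title and directly below it is not visible, so confidence there is lower than for Table 69. Its Week 4 window also matches that of Tables 52, 53, 54 and 59, and on-schedule samples are labelled correctly.

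**The PA has already been reviewed.** This is a fair point. Sections 6.3 and 6.4 say the study was terminated after review of the PA results, so changing PA windows is not cost-free.

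**Conclusion.** The inconsistency is real and should be corrected. It is clearest and most useful to fix in Table 69 LTE, where 6 days' lateness is enough and the LTE analysis was still ahead in this version of the SAP. Table 69 PA and Table 56 PA have the same fault at 13 days. Table 64 departs from the pattern but has little practical effect.

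The size is 25% of each affected interval in Table 69 LTE (7/28), 33% in Table 69 PA (28/84), 25% in Table 56 PA (14/56) and 10% in Table 64 (14/140). These are shares of calendar days, not of samples. How many samples are affected cannot be derived from the SAP.

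The effect is confined to by-visit safety summaries and to the immunoglobulin and B-cell plots; no HBV DNA plot is planned. Shift tables, listings and efficacy tests are untouched. The efficacy windows in Table 51 follow the usual pattern throughout.

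**What to change.** Replace the limits as follows:

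- **Table 69 LTE:** [2;42) Week 4, [42;70) Week 8, [70;98) Week 12, [98;140) Week 16.
- **Table 69 PA:** [154;210) Week 24, [210;294) Week 36, [294;350) Week 48.
- **Table 56 PA:** [21;56) Week 4, [56;126) Week 12.
- **Table 64, PA and LTE, for consistency:** [2;98) Week 4, [98;266) Week 24.

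State in Section 9.7 how the limits are derived, so that the tables can be checked against a rule.

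Apply the corrected limits prospectively to the LTE analysis. For the PA, check whether any record changes visit. If any does, re-run the affected by-visit safety tables and plots, and document the change as made after the PA results were reviewed.

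The LTE cost is a few table cells and no new data. The PA cost is one programming check and, only if records move, a documented revision of outputs already produced.
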